6.2.4 Pharmacokinetics (if applicable)

N/A

6.2.5 Biomarkers (if applicable)

N/a

6.3 Study Procedures

This study aims to enroll 20 adults who report daily mono- e-cigarette use at MUSC and 20 adults who report daily mono- e-cigarette use at Yale (N=40 total). This is a 12-week study with 8 weeks of study drug use (either varenicline or placebo) provided to the enrolled participants. Inclusion/exclusion criteria will be determined via initial online screening and then confirmed with tele-video/phone call final screening. Non-pregnancy verification will be ascertained via remote pregnancy test. If any of these exclusions are endorsed, then the potential participant will not be enrolled into the study. Once screening and informed consent are complete, eligible participants will be randomized to 1 of the following 2 groups:

- 1) VRN + Self-Change Pamphlet

2) Placebo + Self-Change Pamphlet

All participants will be asked to provide assessments (as described below) throughout the sampling process to assess vaping & smoking behavior (if the participant initiates smoking after enrolling in the trial), craving, varenicline/placebo use, use of web-based program, etc.

Randomization: 20 participants per site (MUSC and Yale) will be stratified by status of former or never smoker. Former smoker is defined as an individual who has smoked at least 100 cigarettes in their lifetime but have not smoked in the past 6 months or longer.

Study Details

Guided Self-Change Booklet: This 3-page pamphlet includes information on how to reduce and quit e-cigarettes on their own (on Page 1), how to prevent relapse to combustible cigarettes (for mono vapers who quit combustible cigarettes by vaping; on Page 2), and how to enroll in the online This is Quitting services (described above; on Page 3).

All groups will receive this pamphlet as a brief behavioral component of the intervention. This 2-page pamphlet will include information on how to reduce and quit e-cigarettes on their own on one page, how to prevent relapse to combustible cigarettes (for mono vapers who quit combustible cigarettes by vaping) on the second page, and the third page will contain information about how to enroll in the Truth Initiative/Mayo "This is Quitting" online self-guided e-cigarette treatment program (described below).

Truth Initiative/Mayo "This is Quitting" Program: All participants will be given information about how to enroll in treatment with the This is Quitting Program, which is a free online program that was created by the Truth Initiative in conjunction with Mayo Clinic as a tobacco cessation treatment tool. This program offers online and texting services that assist individuals with their quit attempts for general tobacco use, but they also have specific content/support for vaping. Upon enrolling in the program, the participant is prompted to select a quit date and give their contact information (i.e., email and phone number). The participant is then granted access to the platform that gives them links with cessation tips such as how to deal with cravings, building a support system, dealing with relapse, using medication to help with cessation, etc. The This is Quitting Program also incorporates a text message option. This text message will send the participant 3-4 tobacco cessation related messages per day. If the participant texts "ECIG," a new text thread will be created that will send vaping related messages directly to the participant.

Pharmacotherapy: Twenty participants will be randomized to receive active varenicline. Prior to randomization, the study physician/nurse practitioner/PI [name] conduct a pre-randomization medical review to ensure that they qualify for varenicline based on study eligibility criteria collected during primary (e.g., smoking history, age, medical history, and comorbidities) and secondary screening (psychiatric history, suicidal history, pregnancy status). A summary report that we create within our REDCap screening database, will be delivered electronically to the study physician/nurse practitioners/ PI [name]. They will review each participant's information and will determine whether to 1) accept the individual into the study, 2) reject the individual into the study (i.e., not eligible for varenicline), or 3) ascertain more information from the individual before either the decision to accept/reject the participant. The study physician/nurse practitioners/PI [name] may contact the individual to engage in further clinical interviewing of the potential participant. The disposition of each participant will be tracked within this

screening database, allowing us to complete all CONSORT steps to study flow. The individual will not proceed to randomization and intake until we have signed, explicit documentation from the study physician/nurse practitioners/PI [name] to do so. Thus, these procedures ensure that we retain physician/APRN oversight and approval of varenicline disbursement at the study outset. [name]/APRNs from the Tobacco Treatment Service retains their role in evaluation of adverse events as noted elsewhere within this application.

Upon receipt of medication, the participant will receive a call from our team. This will be a brief orientation call during which they will have an overview of the medication. All participants will be encouraged to start their medication as soon as they receive it and to set a quit date 1-2 weeks from medication initiation. The varenicline prescription will follow the standard induction period: varenicline 0.5 mg once per day for Days 1-3, varenicline 0.5 mg twice per day for Days 4-7, then varenicline 1 mg twice per day (when varenicline reaches peak efficacy for tobacco cessation). Participants will remain on varenicline for 8 weeks total. Dose adjustments (e.g., reduction to 0.5 mg twice per day if 1 mg is not well tolerated) will be allowed at the discretion of the clinical pharmacist/APRN/physician. The entire 8-week supply of varenicline will be shipped at week 1. .

Guided Self-Change Pamphlet: All groups will receive this pamphlet as a brief behavioral component of the intervention. This 3-page pamphlet includes information on how to reduce and quit e-cigarettes on their own (on Page1), how to prevent relapse to combustible cigarettes (for mono vapers who quit combustible cigarettes by vaping; on Page 2), and how to enroll in the online This is Quitting services (described above; on Page 3).

Participant compensation: Participants in this study will have the opportunity to earn up to \$185 for completing their assessments. After completing the randomization and intake during enrollment, they will be paid \$20. Starting on week 1, they will be asked to complete a brief, weekly assessment. Payments for the weekly assessments will increase gradually throughout the treatment phase. You will be paid \$5 for the completing weekly assessments during weeks 1-4, \$10 per assessment for weeks 5-8, \$15 for weeks 9-10, and \$25 for weekly assessment at week 12. End of treatment assessments will be completed at week 12 for a payment of \$35.

	Study Week												
	0	1	2	3	4	5	6	7	8	9	10	11	12
Baseline Assessments	\$20												
Weekly Assessments		\$5	\$5	\$5	\$5	\$10	\$10	\$10	\$10	\$15	\$15	\$15	\$25
End of Follow-up Assessments													\$35

Week Total	\$20	\$5	\$5	\$5	\$5	\$10	\$10	\$10	\$10	\$15	\$15	\$15	\$60
Maximum Total Compensation: \$185													

6.3.1 Study Schedule

1. Intake Procedures (Week 0): Before joining the study, the patient will have first completed a screening visit using a telehealth platform (i.e., Doxy.me, Zoom, or other HIPAA compliant tele-video conferencing software) to obtain their consent using an electronic REDCap consent form) to confirm their eligibility. This research study will use exclusively remote/telehealth procedures as detailed below.

Once the informed consent has been signed, the research staff will ask a few additional questions to determine final eligibility. If they are a female of the age 55 or below, we will send them a pregnancy test in the mail. They will take the at home pregnancy test and complete a secure online survey to verify their test results. After final eligibility has been confirmed, they will be asked to complete some questions about their e-cigarette use.

Randomization (Week 0): They will be randomly assigned, like a flip of a coin, to either the (a) active varenicline medication group, or (b) the placebo group. Neither they nor research staff will know what medication condition to which they have been assigned; only the study pharmacists who prepare and mail their medication will know their medication condition assignment.

Treatment Phase (Week 0-Week 8): They will be sent an 8-week supply of the medication or placebo, along with a guided self-change booklet with information regarding quitting vaping. The study medication will be mailed to them free of charge. Neither they nor your doctor will decide which group they are in. Upon receipt of medication, they will receive a call from our tobacco treatment specialist. This will be a brief orientation call during which the specialist will go over medication use instructions with them. All participants will be encouraged to start their medication as soon as they receive it and to set a quit date 1-2 weeks after receiving the medication.

End of Follow up Phase (Week 12): End of treatment assessments will be completed at week 12.

6.3.2 Informed Consent

Participants will have 2 options to consent into this study: 1) remote consent via a virtual procedure (i.e., Doxy.me or other HIPAA compliant tele-video conferencing software), or 2) remote electronic consent (e-consent) via REDCap combined with a phone call. Informed consent will be maintained in each, allowing (requiring) discussion with study staff to ensure full understanding.

Remote consent via HIPAA compliant tele-video conferencing: This essentially is video, or telephone facilitated live discussion with study staff and potential study participants. After the initial determination of study eligibility, assessed online in our secure survey, participants will be asked about their capacity for virtual procedures (i.e., Doxy.me or other HIPAA compliant tele-video conferencing software), including access to a computer with a webcam and speakers, and compatible internet browser (Doxy.me is currently optimized for Google Chrome & Firefox, with planned expansion to additional browsers). For those who have the

required hardware and software for HIPAA compliant tele-video conferencing, we will offer this option and follow IRB-approved procedures as per precedent. All tele-conferencing signed consent forms will be saved as pdf files within our study records; the participant also receives an electronic copy. Research staff will then have the participant complete the baseline questionnaires.

Remote e-consent via REDCap: This is similar to the above virtual procedures but without the video connection, replaced by live phone call. Participants will link to a REDCap-delivered consent document and will have a concurrent phone discussion with study staff who will provide further details on the study and answer any questions. Like virtual procedures above, these will likely be scheduled with potential participants in advance, i.e., through a consent appointment. The individual would electronically sign the consent form, and this then becomes a part of the research record and like above the participant is given an electronic version of the consent to retain.

For all the above procedures, and throughout the study, the participants will have the research coordinators contact information for any additional support or necessary questions. Anyone who completes a consent form will comprise the consented sample. However, the sample is reduced further to those with whom we can establish phone contact (Day 0; weekly follow-up surveys will begin the following day); i.e., the enrolled sample. This enrolled sample is the intent-to-treat sample.

Although the mode of consent may differ across participants (i.e., Doxy.me vs. REDCap consent) we have taken steps to ensure that all participants will be fully informed of study procedures, including risks/benefits of participation, prior to providing signed consent. We ensure that all potential participants discuss the study with an IRB-approved consenter prior to providing signed consent. All participants, regardless of consenting modality, will be reminded with a study overview at the beginning of the Day 0 phone call and interest in continuing study participation will be confirmed at that point. We believe these methods will maximize opportunities for study participation.

6.3.3 Screening

This study will recruit using advertisements on various media platforms including, but not limited to, Craigslist ads, social media recruitment (e.g., Facebook and Instagram), print, radio, the Hollings and Smilow tobacco treatment services, etc. Since recruitment will also occur through referrals from TTS, medical records will be reviewed for the purposes of screening/recruitment, therefore a waiver of HIPAA authorization will be utilized in this study. Potential participants will complete a pre-screening survey that is linked in the ad. If the individual is deemed eligible, the research staff will conduct a screening appointment via the web/mobile phone with the participant to confirm eligibility. If the research staff deems the individual eligible, our study physician/nurse practitioner from the Tobacco Treatment Service/ PI [name] will review their medical charts and approve their use of varenicline (described in more detail below). After confirming eligibility, the research staff will conduct a full consent and intake via the tele-consent platform (i.e., Doxy.me or other HIPAA compliant tele-video conferencing software) or a link to a REDCap consent form.

6.3.4 Enrollment

Potential subjects will be identified through Tobacco Treatment Service at Yale New Haven Hospital as well as other clinics in Yale-New Haven Hospital. In addition, potential subjects will be identified by responses to community-based advertisements.

Individuals who contact investigators by phone or email or who respond to mobile ads will be directed to complete a 5-minute, web-based pre-screening survey.

Following completion of the pre-screener, research staff will contact potential subjects and inform them of their initial eligibility status. Those who meet initial criteria will attend an intake to provide written informed consent and complete final screening for inclusion/exclusion.

6.3.5 On Study Visits

Assessments	Week 0	Week 4	Week 8	Week 12	Weekly
Demographics	X				
Smoking/Tobacco Use History	X				
Modified Questionnaire on Smoking Urges (QSU)	X		X	X	
E-Cigarette Dependence	X		X		
E-Cigarette Dependence Index	X		X		
Subjective Effects Cigarettes and E-cigarettes	X	X	X		
Patient Health Questionnaire-9 (PHQ9)	X				X*
Wisconsin Withdrawal Scale Brief (WSWS2-B)					
Weekly Electronic Assessments					X
Exit Survey				X	

*bi-weekly

- Baseline (Week 0):
 - Assessment
 - Randomization
- Week 1:
 - Participant sent 1 week supply of 0.5mg and 3-week supply of 1mgOrientation call about medication
 - Weekly assessments
- Week 2
 - Weekly assessments
- Week 3:
 - Weekly assessments
- Week 4:
 - Participant sent second shipment of a 4-week supply of the 1 mg dose.
 - Weekly assessments
- Week 5:
 - Weekly assessments
- Week 6
 - Weekly assessments
- Week 7
 - Weekly assessments
- Week 8
 - Weekly assessments
 - End of treatment phase
- Week 9:
 - Weekly assessments
- Week 10

- Weekly assessments
- Week 11
 - Weekly assessments
- Week 12
 - Weekly assessments
 - Exit survey

6.3.6 End of Study and Follow-up

There will be an end of treatment assessment given at 12 weeks. This survey, designed for the study, will be conducted for all participants. Questions to ascertain participants' reactions to the different intervention conditions (i.e., varenicline, booklet) (e.g., overall satisfaction, perceived helpfulness, etc.), whether they utilized any of the external resources in the booklet (i.e., This is Quitting program) and their reactions, as well as any other use of other medications (e.g., NRT), and behavioral strategies that they used to reduce their e-cigarette use during the study (e.g., titrate e-cigarette nicotine dose, change flavors or switch to unflavored).

6.3.7 Removal of subjects

The Investigators have the right to withdraw a participant at any time. If participants do not follow study instructions, then they may be withdrawn from the study.

This is a voluntary study, in which participants have the right to withdraw at any time. If the participant decides to withdraw at any point, they can inform the research staff. No further data will be collected, and correspondents will stop. Any data collected up to that point will remain in study.

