Other contraindications for varenicline include suicidal ideation.²¹ Suicidality will be assessed at prior to randomization and during the follow-up assessments. If an individual endorses suicidality during the pre-randomization screening, they will be marked as ineligible for the study. This will be assessed using the PHQ9 toolkit for suicide ideation (refer to assessments section). An alert is programmed into the REDCap system that if an individual indicates an active plan to either physically harm or kill themselves, an alert will be sent to the study team. They will then be contacted by our clinical team to complete a risk assessment over via phone. A member of the clinical team will query the participant for details regarding the suicidal ideation, including a likelihood of harming oneself imminently and a plan for committing suicide. If the participant reports an imminent likelihood of harming him/herself or a plan for committing suicide, the clinical team member will call emergency services and will remain on the phone with the participant until emergency services arrive. In the event that the participant expresses an imminent likelihood of harming him/herself, and

the connection is lost, emergency services will be contacted to provide emergency services with the participant's contact information, including address. If the participant is not in imminent danger, the clinical staff will provide referrals for local mental health resources and/or instruction to go to the ED or call 911 should suicidal ideation worsen. The clinical team member will suggest that the participant seek treatment and then will follow-up with the participant via phone one week later.

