In the event that a participant endorses suicidal ideation but is not responsive to clinical staff's phone call within 48 hours, the participant will be emailed a list of local mental health resources and will suggest that the participant seek additional treatment. The email will also ask that the participant respond to the clinical staff either via phone or e-mail within 24 hours to confirm receipt of the treatment referrals. Should the participant not respond to the clinical staff's email within an additional 48 hours (4 days from completion of the assessment) and endorse "Several days", "More than half the days" or "nearly everyday" to "Thoughts that you would be better off dead or of hurting yourself in some way" on the PHQ9 suicidality toolkit at study screening, emergency services will be contacted and will be provided with the participant's name and address.

We will utilize the PHQ9 assessment to track depression and suicidal ideation during the baseline assessments. If suicidal ideation is endorsed, an automated "red flag" will be processed through our REDCap database. This red flag will indicate either a a) clinically significant increase in total PHQ scoring with an overall score of at least 15 (>5 point increase from baseline and resulting score >15), OR b) any value >0 for item 9/suicidal ideation). The red flag indicators will be monitored daily by our clinical team and will be met with the appropriate measures. These measures are based on prior MUSC-IRB approved protocols of varenicline (i.e., the STARS Pro00098479).

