6.2 Assessments

6.2.1 Efficacy

Study Assessments

The following tools will be used for the assessments conducted at baseline (week 0) and end of follow-up (Week 0, 8 & 12).

Demographics (Week 0): This questionnaire will collect basic demographic information for each subject including gender, ethnicity/race, employment status, etc.

Smoking/Tobacco Use History (Week 0): This will collect basic info about smoking and smoking cessation history, prior varenicline use, e-cigarette history, tobacco and nicotine product flavor preference, etc.

Modified Questionnaire on Smoking Urges (QSU) (Week 0, 8 & 12): This 3-item assessment is used to examine smoking related urges such as desire to smoke, anticipation of immediate positive outcome, etc.³¹E-cigarette Dependence (Week 0 & 8): The NIH Patient-Reported Outcomes Measurement Information System (PROMIS) measure for daily smokers has also been adapted to measure for use of other tobacco products.^{30, 40} This is a 4-item e-cigarette dependence questionnaire that measures withdrawal and craving.

E-cigarette Dependence Index (Week 0 & 8): This is a 10-item e-cigarette dependence questionnaire that measures difficulty quitting, withdrawal and cravings.⁵⁷

Subjective Effects Cigarettes and E-cigarettes (Week 0, Week 4): Participants will report on subjective evaluation about cigarettes and e-cigarettes. Subjective evaluation includes items derived from the Modified E-Cigarette Evaluation Questionnaire (meCEQ)⁵⁸ that have also been adapted for alternate tobacco products. It measures the degree to which participants experience reinforcing effects from smoking and e-cigarettes. The scale yields five clusters or domains: Smoking Satisfaction, Psychological Reward, Aversion, Enjoyment of Respiratory Tract Sensations, and Craving Reduction.⁵⁶

Patient Health Questionnaire-9 (PHQ9) (Week 0 and Bi-Weekly): which assesses for depression and includes an item on suicidal ideation.⁵⁰

Wisconsin Withdrawal Scale Brief (WSWS2-B): This 6-item scale assesses current symptoms of nicotine withdrawal including cravings and irritability.⁵⁹

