The data will be stored on secured server, laptop computer and desktop computer. The data will be stored in a locked room for 7 years after the final data is collected. After this point, the Data Manager and Principal Investigator, [name], will oversee the process in which data is destroyed or de-identified.

Several steps will be taken to safeguard the confidentiality of subjects and their data. All research data that is collected will be assigned a study participant number and that number will only identify participants in digital databases. The names of participants will not be associated with this data and assessments will be maintained according to participant study number. A master list connecting participant study numbers to participant names will be kept in a locked file cabinet where it can only be accessed by senior level project staff. Any information published as a result of the study will be such that it will not permit identification of any participant.

Right to privacy for participation in this research will be protected through alphanumeric coding of data (in place of names) and proper storage of research records, including treatment exit interviews. Collected materials will be maintained via an alphanumeric reference system maintained by [name]. Participants' names will appear only on the compound authorization form, and a master list maintained in a physically locked file that is separate from research data. Our data collection and management procedures are fully compliant with HIPAA. Access will be limited to personnel intimately involved in the study. A Certificate of Confidentiality will also be obtained. However, participants will also be told that if they present with suicidal or homicidal ideation and/or report any form of child/elder abuse or report plans to damage property then we will have to report this to the appropriate authorities and/or provide them with referrals for immediate treatment. Electronic data will be de-identified, and password protected. Only members of the study team will have access to the physical or electronic data.

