7.9 Data or Specimen Storage/Security

Several steps will be taken to safeguard the confidentiality of subjects and their data. All research data that is collected will be assigned a study participant number and that number will only identify participants in digital databases. The names of participants will not be associated with this data and assessments will be maintained according to participant study

number. A master list connecting participant study numbers to participant names will be kept in a locked file cabinet where it can only be accessed by senior level project staff. Any information published because of the study will be such that it will not permit identification of any participant.

Research records are maintained under the person's name, but the study number is not entered anywhere into a medical record. Right to privacy for participation in this research will be protected through coding of data and proper storage of research records. The Principal Investigators will maintain a list of IDs and the corresponding names in a locked research cabinet. Consistent with mandated reporting requirements for health providers, we advise participants that in the case of child abuse or neglect, threat of injury to self or others, or intention to destroy property, that we may need to intervene and report that information to the proper authorities. Subjects will be informed of this limit to confidentiality as it is stated in the informed consent document.

The data will be stored in a locked room for 6 years after the final data is collected. The PI and the research staff will have access to PHI. Organizations that have a responsibility for protecting human participants, including the MUSC/Yale IRB, may have access to subjects' medical records containing PHI. Additionally, the funding source may have access to subjects' medical records containing PHI.

Trained research staff will administer assessments and collect measurements. They will enter data directly into a secure electronic database, which will be backed up on a secure, password protected Yale University network drive. De-identified data will be stored in the database and only accessible by research staff using a password protected login. All data with identifiable information will be stored in locked file cabinets in locked offices and will only be accessible by research staff.

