In the event that a participant endorses suicidal ideation but is not responsive to clinical staff's phone call within 48 hours, the participant will be emailed a list of local mental health resources and will suggest that the participant seek additional treatment. The email will also ask that the participant respond to the clinical staff either via phone or e-mail within 24 hours to confirm receipt of the treatment referrals. Should the participant not respond to the clinical staff's email within an additional 48 hours (4 days from completion of the assessment) and endorse "Several days", "More than half the days" or "nearly everyday" to "Thoughts that you would be better off dead or of hurting yourself in some way" on the PH-Q suicidality toolkit at study screening, emergency services will be contacted and will be provided with the participant's name and address.

We will utilize the PHQ9 assessment to track depression and suicidal ideation during the baseline assessments. If suicidal ideation is endorsed, an automated "red flag" will be processed through our REDCap database. This red flag will indicate either a a) clinically significant increase in total PHQ scoring with an overall score of at least 15 (>5 point increase from baseline and resulting score >15), OR b) any value >0 for item 9/suicidal ideation). The red flag indicators will be monitored daily by our clinical team and will be met with the appropriate measures. These measures are based on prior MUSC-IRB approved protocols of varenicline (i.e., the STARS Pro00098479).

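### Section 6.3.7 stops contact at withdrawal with no safety exception, which, taken literally, cancels the promised one-week suicidality follow-up call

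*Combined protocol and SAP*

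**What the plan says.** Section 6.3.7 lets a participant leave at any point by telling the research staff. It then states: "No further data will be collected, and correspondents will stop". Data already collected are kept. The section gives no exception for open safety matters. It separately allows the investigators to remove a participant but does not say what contact follows in that case.

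The suicidality procedure is set out in section 3.2.1 and repeated in 5.1, 6.1.3 and 7.12. On timing, 3.2.1 says: "Suicidality will be assessed at prior to randomization and during the follow-up assessments". The instrument is the PHQ-9, "which assesses for depression and includes an item on suicidal ideation" (section 6.2.1), given at week 0 and bi-weekly (6.2.1 and the table in 6.3.5). The procedure has two branches:

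- **Participant reached by phone.** The clinical team makes a risk assessment. If danger is imminent, emergency services are called during that contact. Otherwise staff give referrals and emergency instructions, suggest treatment, and "then will follow-up with the participant via phone one week later".
- **Participant not reached within 48 hours.** Under 7.12, "the participant will be emailed a list of local mental health resources". Section 3.2.1 adds: "The email will also ask that the participant respond to the clinical staff either via phone or e-mail within 24 hours".

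Two other sections bear on the point. Section 7.3 says that if a participant presents with suicidal ideation, "we will have to report this to the appropriate authorities and/or provide them with referrals for immediate treatment". Section 7.9 tells participants, for a threat of injury to self, "that we may need to intervene and report that information to the proper authorities".

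**The concern.** The one-week call is intended for someone who has reported suicidal thoughts and was judged safe enough not to need emergency services that day. If that person withdraws during the week, the protocol gives two incompatible instructions. Staff who follow 6.3.7 do not call. Staff who follow 3.2.1 call and depart from 6.3.7. With two sites, the answer may differ by site.

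Section 6.3.1 describes the study as conducted entirely by remote means, so no clinic visit can serve as a fallback check. A participant who leaves during treatment may also still hold study capsules: 6.1.3 and 6.3 ship the full 8-week supply at week 1, while 6.3.5 describes two shipments. Section 6.3.7 gives no advice about stopping them.

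What is at stake is the safety of an individual participant. The trial's estimates are not in question.

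**Working it through.** The plan states no figure to reproduce. The check is mainly a comparison of texts, followed by a short calculation of how long the overlap lasts.

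1. **Trigger of the stop rule.** In 6.3.7 the rule follows withdrawal chosen by the participant, at any time.

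2. **Can suicidality follow-up be open in an enrolled participant?** Endorsing suicidality at screening makes a person ineligible, so only later assessments count. Section 3.2.1 places assessment in follow-up as well, and the PHQ-9 is scheduled bi-weekly. One sentence in 3.2.1 speaks of PHQ-9 tracking at baseline. However, the red flag defined there includes a rise from baseline, which can only occur later. The answer is yes.

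3. **Does the one-week call depend on staying in the study?** None of its four statements (3.2.1, 5.1, 6.1.3, 7.12) makes it conditional on enrolment or mentions withdrawal.

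4. **Is there an exception elsewhere?** Sections 6.2.3 and 6.4.2 (adverse events), 7.3 and 7.9 (confidentiality), and 7.11 to 7.14 (monitoring, modification, discontinuation) contain none tied to withdrawal. Sections 7.3 and 7.9 keep a duty to refer, report or intervene, but do not say that the call continues.

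5. **Length of the overlap.**
   - From the risk call to the follow-up call: 7 days (3.2.1).
   - Counted from the PHQ-9, if the risk call connects only at the 48-hour limit: 2 + 7 = 9 days.

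6. **Occasions on which it can arise.** Assume that bi-weekly means every 14 days.
   - Post-baseline PHQ-9s in 12 weeks: 12 / 2 = 6 (weeks 2, 4, 6, 8, 10, 12).
   - In the 8-week treatment phase: 8 / 2 = 4.
   - Followed by another PHQ-9: 6 − 1 = 5, because week 12 is the last.
   - Share of the interval to the next PHQ-9, for those 5: 7/14 = 50%, or 9/14 = 64% if the wait for the risk call is included.

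These shares are conditional on a flag that leads to the one-week call. That link is partly inferred: 3.2.1 attaches the alert and risk call to an active plan of self-harm, and promises only appropriate measures for the broader red flag. The expected number of participants cannot be computed, because the documents give neither a withdrawal rate nor an ideation rate.

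**The case against.** The strongest reply is that the conflict exists only on a literal reading. The stop sentence couples contact with data collection and sits among the study procedures, so its natural object is survey prompts and adherence texts. The suicidality steps are clinical duties in the risk and safety-monitoring sections, and a general withdrawal sentence would not ordinarily cancel a specific safety procedure. Staff would probably let safety prevail, and 7.3 and 7.9 point that way. This stands as a forecast of behaviour, but the protocol does not say it, and staff should not have to infer which instruction to break.

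Second, the main protection comes before the disputed contact. Emergency help, or referrals and emergency instructions, is given in the risk call itself; only the later check-in is exposed. This stands in full.

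Third, the consent form could not be seen and may deal with withdrawal. Section 7.9 says the form states the limit to confidentiality, so it covers at least neighbouring ground. This also stands.

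Fourth, ending contact on request respects voluntary participation. That is a reason to make the exception depend on agreement. It does not justify leaving the protocol silent.

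A reader might also infer that both the call and the email are lost for every flag. They are alternatives: the email is for people who do not answer, the one-week call for people who were reached. The email overlap is nearly empty, since it needs someone who does not answer the risk call yet tells staff of the withdrawal.

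**Conclusion.** The point holds as a narrow safety gap centred on the one-week call. Section 6.3.7 states a rule that, followed as written, drops a contact promised in four other sections, and no text says which prevails. The exposure is 7 days per follow-up, with up to 6 post-baseline PHQ-9 occasions if bi-weekly means every two weeks. The number of participants affected is unknown and may be small in a pilot of 40. The conclusion assumes that the consent form does not already settle the matter.

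Stronger readings are not supported:

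- A reader might infer that withdrawal cuts a suicidal participant off from emergency help. It does not: imminent risk is handled within the risk call, and 7.3 and 7.9 are not tied to enrolment.
- A reader might infer that the later emergency-services step for non-responders is also cancelled. In 3.2.1, 6.1.3 and 7.12 that step is worded for endorsement at screening, so it is not relied on here.
- A reader might infer that contact also stops after removal by the investigators. Section 6.3.7 is silent on that case.
- A reader might infer damage to the abstinence or adverse event comparisons. This point has no effect on analysis, power or bias.

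**What to change.** Amend 6.3.7 to say that withdrawal ends research data collection and routine study contact but that, with the participant's agreement, open suicidality follow-up under 3.2.1 is completed. That wording removes the conflict.

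Three additions are sensible in the same amendment, though they do not arise from the contradiction:

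- With the participant's agreement, follow any ongoing serious adverse event until it has resolved or is stable.
- At withdrawal, have staff advise the participant about stopping the remaining study capsules.
- Apply the same text to removal by the investigators.

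Match the consent form if it does not already say this.

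The cost is a few sentences in an IRB amendment and a few extra calls by existing staff. Some participants will decline the contact. Their refusal should be recorded and respected, and for them the change adds nothing beyond the offer.
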